4.2 Study Population

The Mother-baby link includes 1,071,379 children born from Jan 1st 1990 to June 30th 2016.

Inclusion Criteria:

- Children whose mother was prescribed an only monotherapy of macrolide or penicillin during pregnancy (between 5 Gestational Week [GW] and delivery)
- Children who registered with the general practice (GP) within 6 months of birth
- Children whose mother was aged 14 to 50 years at delivery and had been registered with GP from at least 50 weeks before estimated conception date to delivery

Exclusion Criteria:

Children with known chromosomal abnormalities or with fetal exposure to known teratogenic medications (warfarin, angiotensin-converting enzyme (ACE) inhibitors, antineoplastic agents, isotretinoin, misoprostol, and thalidomide).

Children will be followed from birth to death, end of follow-up (June 30th, 2016), or age 14, whichever came first.

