4.3 Study Variables

4.3.1 Exposure

The exposure group will include children whose mother were prescribed an only monotherapy of macrolide antibiotics from 5 GW to delivery (hereafter, “during pregnancy”). A monotherapy is defined as one or more consecutive prescriptions for a single antibiotic (i.e. same drug substance) separated by no more than 30 days and uninterrupted by prescriptions for other antibiotic drug substances. The macrolides prescription is identified using a drug code list based on chapter 5.1.5 of the British National Formulary. The date of first prescription is used as the index date. The reference group includes children whose mothers were exposed to an only monotherapy of penicillins during pregnancy. Preliminary analysis shows that 81% of all antibiotic prescriptions were monotherapies. We further divide the time window into 1) 5GW to 13GW (29 Gestational Day [GD] to 91GD, hereafter, “1st trimester”), the critical period for most major malformation, and 2) 14GW to delivery (hereafter, “2nd–3rd trimester”).(21) The negative control cohort (see “4.4.2 Sensitivity analyses [1]”) includes children of mothers prescribed an only monotherapy of macrolides or penicillins during 10-50 weeks prior to conception and are not included in the study cohort.

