- a Read codes for hypertension and associated diagnoses (including pre-eclampsia, eclampsia and HELLP syndrome), or
- a prescription for hypertension drugs from sections 2.2 and 2.5 of the BNF. This variable identified mothers with both treated and untreated hypertension in pregnancy.

7) **Diabetes**

Measurement from 50 weeks prior to delivery:

- a Read code for type I, type II, or gestational diabetes;
- two or more prescriptions for anti-diabetic medication; or
- laboratory tests indicative of diabetes (defined as ≥ 2 abnormal glucose tests, fasting glucose >7.0 millimoles per litre [mmol/L] or >126 milligrams per decilitre

[mg/dL], plasma glucose after glucose tolerance test >11.1 mmol/L or 200mg/dL, glycated haemoglobin \geq 6.5%, or with diabetes annual review).

8) Epilepsy

Measurement from 50 weeks prior to delivery: 2 prescriptions of antiepileptic drugs (AEDs) within 4 months or \geq 1 diagnosis

9) Depression

Measurement from 50 weeks prior to delivery: \geq 2 occurrences of diagnostic code, treatment code or symptom

10) Anxiety

Measurement from 50 weeks prior to delivery: \geq 2 occurrences of diagnostic code, treatment code or symptom

11) Treatment of chronic medical conditions during pregnancy

Measurement during pregnancy: two or more prescriptions (on separate days during pregnancy and not more than four months apart) for drugs from the same BNF section or paragraph. Drugs used to treat common conditions in pregnancy such as reflux (BNF section 1.2), nausea and vomiting (BNF section 4.6), and constipation (BNF section 1.3) were not included.

12) Potentially fetal-damaging infections during pregnancy.

Mothers are classified as having a potentially fetal-damaging infection in pregnancy if they had recorded at any time during their pregnancy, a Read code for a diagnosis or a laboratory test confirming any of the following infection: genitourinary infection, "TORCH" (Toxoplasmosis, Other agents such as HIV, Rubella, Cytomegalovirus and Herpes simplex) and sexually transmitted infections (STIs). "TORCH" and STIs have long been known as important risk factors to adverse pregnancy outcomes and teratogenic pathogens. (22, 23) Intrauterine infection has been recognised as an important mechanism of disease in preterm labor. (24) Hyelonephritis and bacteriuria have also been linked with preterm labor and low birthweight. (25)

3. Neonatal variables

13) Baby gender

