4.4 Analyses

4.4.1 Statistical methods

Standardized differences will be used to assess covariate balance between the macrolides group and the penicillins group; meaningful imbalances are defined by an absolute standardized difference of more than 0.1.(30) For neurodevelopmental disorders, absolute rates of outcomes and unadjusted hazard ratios with 95% confidence intervals will be calculated. For malformations, absolute risks of outcomes and unadjusted risk ratios with 95% confidence intervals, will be calculated. Exposure propensity scores will be estimated as the predicted probability of receiving the macrolides prescription (vs. penicillins), conditional on the covariates described above, with the use of logistic-regression models. For each estimated propensity score, the population in the nonoverlapping areas of the propensity-score distributions will be trimmed, and 50 strata will be created on the basis of the distribution of the treated women.(31) Weights for the reference group will be calculated according to the distribution of the treated women among propensity-score strata. We then use the weight to estimate adjusted baseline characteristics, and adjusted hazard ratios (in Cox proportional hazard models with weight statement for neurodevelopmental disorders) or risk ratios (in log-binomial model with weight statement for malformations) as well as their 95% confidence intervals. To account for the clustering of siblings and multiple births within mother, robust standard errors will be estimated. The analyses will be conducted using RStudio version 3.5.1.. No adjustment will be made for multiple comparisons, and results for comparisons of exposure timing and subgroup analysis should be interpreted as exploratory.

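### Covariate item 11, as written, counts repeat prescriptions of the study macrolide or penicillin as treatment of a chronic condition, and that flag enters the propensity score

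*Combined protocol and SAP*

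**What the plan says.** Section 4.3.3, item 11 is headed as treatment of chronic medical conditions during pregnancy. Its operational rule is "two or more prescriptions (on separate days during pregnancy and not more than four months apart) for drugs from the same BNF section"; a shared BNF paragraph also suffices. The item leaves out drugs for common conditions in pregnancy, with three examples: "such as reflux (BNF section 1.2), nausea and vomiting (BNF section 4.6), and constipation (BNF section 1.3) were not included".

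Section 4.2 admits "Children whose mother was prescribed an only monotherapy of macrolide or penicillin during pregnancy", counted from 5 gestational weeks to delivery. Section 4.3.1 defines the course: "A monotherapy is defined as one or more consecutive prescriptions for a single antibiotic (i.e. same drug substance) separated by no more than 30 days", with no other antibiotic substance in between. The first prescription sets the index date. On drug codes the section says: "The macrolides prescription is identified using a drug code list based on chapter 5.1.5 of the British National Formulary".

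Section 4.4.1 then uses the covariates: "Exposure propensity scores will be estimated as the predicted probability of receiving the macrolides prescription (vs. penicillins), conditional on the covariates described above". The penicillin group is reweighted: "Weights for the reference group will be calculated according to the distribution of the treated women among propensity-score strata". On balance, "meaningful imbalances are defined by an absolute standardized difference of more than 0.1".

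**The concern.** The exposure and one of the confounders are built from the same records. A mother who receives a second prescription of her study antibiotic within 30 days satisfies item 11 without having any chronic condition. That second prescription is part of the exposure course and comes after the index date, so it is not a baseline characteristic.

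The penicillin group is then weighted to match the macrolide group on a flag that mixes true chronic treatment with repeat exposure. If repeat prescribing differs between the groups, weighting can create an imbalance in true chronic treatment where there was none. If true chronic treatment differs, weighting removes only part of the difference. At stake is how well one covariate does its job in the adjusted hazard ratios and risk ratios.

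**Working it through.** **Step 1: do the definitions overlap?**

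| Requirement of item 11 | Study course with two or more prescriptions on separate days |
|---|---|
| Same BNF section or paragraph | Same substance, from one code list (5.1.5 for macrolides) |
| During pregnancy | 5 gestational weeks to delivery |
| Separate days | Met by assumption; single-prescription courses are unaffected |
| Not more than four months apart | Gaps of at most 30 days |
| Not in a named exclusion (1.2, 4.6, 1.3) | Antibacterials are not named |

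Every such course meets the rule as written. If the sole-monotherapy criterion means no other antibiotic course in the window, any antibacterials that trigger item 11 there are the exposure itself.

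**Step 2: inputs.** The documents give neither the share of courses with two or more prescriptions nor the prevalence of chronic treatment. The 81% in Section 4.3.1 is the share of antibiotic prescriptions that were monotherapies, which is a different quantity. Everything below is therefore assumed, except the group sizes and baseline risks in Step 5. There is no figure in the plan to reproduce.

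Let c be the true prevalence of chronic treatment and r the repeat rate, with M for macrolide and P for penicillin. Repeats are taken as independent of chronic disease and of outcome, item 11 as the only covariate, and the drug as having no effect.

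- Flag prevalence: F = c + (1 − c)r
- Chronic share in the penicillin group after weighting on the flag: w = F_M × c_P / F_P
- Standardized difference in true chronic treatment after weighting: (c_M − w) / √{[c_M(1 − c_M) + w(1 − w)]/2}
- Adjusted risk ratio, where R is the outcome risk ratio for chronic disease: [1 + (R − 1)c_M] / [1 + (R − 1)w]

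Worked case, c = 0.20 in both groups, r = 0.10 v 0.05: F = 0.20 + 0.80 × 0.10 = 0.28 v 0.20 + 0.80 × 0.05 = 0.24. Then w = 0.28 × 0.20 / 0.24 = 0.2333, and with R = 2.0 the adjusted risk ratio is 1.20 / 1.2333 = 0.973.

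**Step 3: results with c = 20% in both groups** (absolute standardized differences)

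| Repeat rate, M v P | Flag, M v P | Flag difference, unweighted | w | Difference in true chronic treatment, weighted | Adjusted RR, R = 2.0 | R = 1.5 |
|---|---|---|---|---|---|---|
| 10% v 5% | 28.0% v 24.0% | 0.091 | 23.3% | 0.081 | 0.973 | 0.985 |
| 5% v 10% | 24.0% v 28.0% | 0.091 | 17.1% | 0.074 | 1.024 | 1.013 |
| 20% v 10% | 36.0% v 28.0% | 0.172 | 25.7% | 0.136 | 0.955 | 0.975 |
| 2% v 1% | 21.6% v 20.8% | 0.020 | 20.8% | 0.019 | 0.994 | 0.997 |
| 10% v 10% | 28.0% v 28.0% | 0 | 20.0% | 0 | 1.000 | 1.000 |

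The flag itself is exactly balanced after weighting in every row. If true chronic treatment is 25% v 20% and repeats are 10% in both groups, then F = 0.325 v 0.28 and w = 0.2321. A standardized difference of 0.042 remains, and a risk ratio of 1.25/1.2321 = 1.014 is left of a crude 1.25/1.20 = 1.042 (R = 2.0).

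**Step 4: when does the hidden difference reach the plan's 0.1?** With c = 20% and the macrolide rate higher, it does so at 6.4% v 1%, 11.2% v 5%, 17.2% v 10% and 29.3% v 20%. The rate ratios are 6.4, 2.2, 1.7 and 1.5, so no single multiple serves as a rule. The unweighted flag differences at these points are 0.103, 0.113, 0.126 and 0.153.

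**Step 5: scale.** Section 4.5 gives about 10,000 and 100,000 pregnancies. An approximate 95% interval factor is exp{1.96√(1/a − 1/10,000 + 1/b − 1/100,000)}, where a and b are the expected case counts. At baseline risk 0.02 (a = 200, b = 2,000) it is 1.155; at 0.002 (a = 20, b = 200) it is 1.583. The largest shift in the table, 0.955, is a factor of 1/0.955 = 1.05 and lies inside both.

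**The case against.** The strongest reply is that item 11 is about chronic conditions, that its exclusions are introduced as examples, and that infection has its own covariate (item 12). Antibiotics for acute infection could be meant to fall in the excluded class, and the operative code list is not in the documents. This stands as far as it goes: the fault may lie in the wording and not in the analysis. It lowers confidence, but the text still gives no such exclusion, and an analyst who follows the rule as written would set the flag.

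Second, no impact is shown. That is correct. All inputs are assumed, and the shift is nil when repeat rates and chronic prevalence are each equal between groups. The model is also simple. Repeat courses may mark more severe or persistent infection, in which case part of what the flag captures could be useful adjustment. Hypertension, diabetes, epilepsy, depression and anxiety also enter the score separately. The illustrated values therefore cannot be called an upper bound.

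Third, a reader might infer that the planned balance check is blind to the problem. That goes too far. Section 4.4.1 describes the check before it introduces the propensity score, so an unweighted comparison is a natural reading, and in each Step 4 case the unweighted flag difference exceeds 0.1. Such a check might show the imbalance in the flag, though not its cause. What does hold is that a weighted check on the flag would not show the resulting imbalance in true chronic treatment.

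**Conclusion.** The point holds as one of definition: item 11 as written codes a multi-prescription study course as treatment of a chronic condition and passes it to the propensity score. It is minor, and confidence is moderate because an unstated exclusion in the code list is possible. Neither size nor direction can be computed from the documents. Under the assumptions in the working, adjusted risk ratios run from 0.955 to 1.024 with R = 2.0.

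A reader might go on to infer that covariate windows running past the index date bias the comparison in general. The documents do not support that. They propose no path from macrolide rather than penicillin to the conditions concerned, and no bias can be calculated from them. Section 4.3.3 also shows that mediators were considered, since gestational age at delivery and Apgar score are left unadjusted. The conclusion here is confined to item 11.

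**What to change.** 1. State in item 11 that the macrolide and penicillin prescriptions that define exposure do not count towards the flag, or that antibacterials in general do not. If the code list already does this, the sentence only records it.
2. Report, by exposure group, the share of mothers with two or more prescriptions in the exposure course. This supplies the missing input and shows whether the rule as written would have mattered.

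The cost is one sentence and one table row from data already held. There are two drawbacks. If all antibacterials are excluded, a few women on long-term antibiotics for a chronic condition lose the flag. Any adjustment for infection severity that the flag gave by accident is also lost.

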4.4 Analyses

4.4.1 Statistical methods

Standardized differences will be used to assess covariate balance between the macrolides group and the penicillins group; meaningful imbalances are defined by an absolute standardized difference of more than 0.1.(30) For neurodevelopmental disorders, absolute rates of outcomes and unadjusted hazard ratios with 95% confidence intervals will be calculated. For malformations, absolute risks of outcomes and unadjusted risk ratios with 95% confidence intervals, will be calculated. Exposure propensity scores will be estimated as the predicted probability of receiving the macrolides prescription (vs. penicillins), conditional on the covariates described above, with the use of logistic-regression models. For each estimated propensity score, the population in the nonoverlapping areas of the propensity-score distributions will be trimmed, and 50 strata will be created on the basis of the distribution of the treated women.(31) Weights for the reference group will be calculated according to the distribution of the treated women among propensity-score strata. We then use the weight to estimate adjusted baseline characteristics, and adjusted hazard ratios (in Cox proportional hazard models with weight statement for neurodevelopmental disorders) or risk ratios (in log-binomial model with weight statement for malformations) as well as their 95% confidence intervals. To account for the clustering of siblings and multiple births within mother, robust standard errors will be estimated. The analyses will be conducted using RStudio version 3.5.1.. No adjustment will be made for multiple comparisons, and results for comparisons of exposure timing and subgroup analysis should be interpreted as exploratory.

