Prompt and adequate treatment for infection during pregnancy is vital given the well-established association between maternal infection during pregnancy and adverse birth outcomes, including miscarriage and stillbirth.(17) More evidence is needed on whether there is a causal association between maternal macrolide antibiotics treatment during pregnancy and adverse child outcomes.

2. Objectives

We will conduct a population-based cohort study to evaluate the association between the macrolide antibiotics prescription in pregnancy and adverse child outcomes (neurodevelopmental disorders and major malformation (overall and system-specific)) (**primary analysis**), and to examine this association by macrolides subtypes and length of prescriptions (**subgroup analysis**).

3. Data source

We will use the Clinical Practice Research Datalink (CPRD), a UK-representative database which captures prospective, anonymised data on prescriptions, diagnoses, and symptoms records in primary care.(18) A Mother-baby link was built within CPRD using family ID, practice ID, and date of birth/delivery, with details reported elsewhere.(19, 20) For each mother-baby pair, a delivery date was estimated (Appendix).

4. Methods

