4.3.2 Outcome

Based on previous evidence from experimental and epidemiological studies, we hypothesized that short-term fetal hypoxia induced by fetal arrhythmia could possibly be the underlying mechanism of observed adverse effects of macrolides.(22) We therefore include outcomes which could potentially result from short-term fetal hypoxia, i.e. neurodevelopmental disorders (CP, epilepsy, attention-deficit/hyperactivity disorder (ADHD) and autism spectrum disorder (ASD)) and major congenital malformation (malformation overall and system-specific malformations).

Neurodevelopmental disorders (CP, epilepsy, ADHD and ASD) are defined as the time to the first Read code or prescription indicating the outcomes by 14 years old. We have identified CP cases from informative prescription or Read codes using the Random Forest approach and were validated by a paediatric-neurologist blinded to the prenatal antibiotics exposure.(23) Other neurodevelopmental disorders (epilepsy, ADHD and ASD) will be identified with previously validated criteria using diagnostic codes and/or prescriptions (table 1). (24-26)

Major malformations will be identified from the European Surveillance of Congenital Anomalies (EUROCAT).(27) We will exclude musculoskeletal malformations (e.g. Club foot, knock-knee and hip dislocation) because they are not reliably recorded in GP records.(28) We also exclude children with known chromosomal abnormalities and children whose mother were exposed to known teratogenic medications (warfarin, angiotensin converting enzyme (ACE) inhibitors, antineoplastic agents, isotretinoin, misoprostol, and thalidomide). Any of the remaining 11 system-specific malformations are defined as major malformation overall, identified from child GP records up to 3 years old using Read codes which are mapped to the tenth edition of the International Classification of Diseases (ICD–10) code lists in EUROCAT (Table 1).(27) Five system-specific malformations (nervous, cardiovascular, digestive, genital tract, and urinary tract) were included which met the power criterion using the EUROCAT prevalence table.(29) (see “4.5 Power analysis”)

Table 1. Outcome identification.

Outcome	Case identification criteria
Cerebral palsy	Method based on predictor selection and prediction (23)
Epilepsy	2 prescriptions of antiepileptic drug (AED, identified based on British National Formula Chapter 4.8) within 4 months or ≥ 1 diagnosis

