4.3.3 Covariates

We will control the covariates which are potential risk factors for adverse child outcomes. These include: 1) maternal characteristics at baseline (i.e. age at child birth, problematic alcohol use, illicit drug use, recent tobacco use, and obesity); 2) pregnancy related variables (i.e. birth year, parity, multiple birth, hypertension, diabetes, epilepsy, depression, anxiety, maternal chronic medical conditions during pregnancy, potentially fetal-damaging maternal infection during pregnancy, and baby gender) (details given below). Gestational age at delivery and Apgar score after birth are considered mediators on the pathway for the association between prenatal antibiotics exposure and adverse child outcomes and therefore not adjusted.

1. *Maternal variables*

1) **Maternal age (at birth)**

By 5 year categories.

2) **Maternal life style:**

a. Problematic alcohol use:

Most recent record between 10 years prior to and during pregnancy:

- a Read code indicating alcohol misuse; or
- a prescription for disulfiram or acamprosate; or
- self-reported average weekly alcohol intakes of between 14-500 units of alcohol a week.

b. Illicit drug use:

Most recent record between 10 years prior to and during pregnancy:

- a read code for drug use, addiction, and overdose; or
- a prescription for methadone treatment

c. Recent smoking/tobacco use:

Most recent record between 3 years prior to and during pregnancy:

- self-reported daily cigarette consumption of 1-100 cigarettes per day unless there was evidence of smoking cessation; or
- a read code indicating tobacco consumption; or
- a prescription to assist smoking cessation

d. Obesity

Most recent record from 3 years prior to the end of 1st trimester:

A read code for obesity (or a BMI of ≥ 30 kg/m² - either directly entered or calculated from the most recent height measurement and median pre-pregnancy weight after outliers, i.e. height outside the range 1-2m and weight outside the range 35-300kg, were removed).

2. *Pregnancy related variables*

3) **Baby birth year**

Grouped into categories of 5 calendar years.

4) **Parity**

Categorised as "0", and " ≥ 1 ".

5) **Multiple births**

Categorize the baby as "singleton", or "(one of the) twin, triplets, or quadruplets".

6) **Hypertension**

Measurement from 50 weeks prior to delivery:

- systolic and diastolic blood pressure was above 140mmHg and 90mmHg, respectively, or

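### Practices prescribe the antibiotic and record the outcomes, yet no planned analysis compares children within a practice; a cheap sensitivity analysis would test this

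*Combined protocol and SAP*

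**What the plan says.** Section 3 describes the database as holding "prospective, anonymised data on prescriptions, diagnoses, and symptoms records in primary care". It adds that "A Mother-baby link was built within CPRD using family ID, practice ID, and date of birth/delivery", so a practice identifier exists and mother and child are tied through it.

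Section 4.3.2 takes the outcomes from the same type of record. Malformations are "identified from child GP records up to 3 years old using Read codes". Neurodevelopmental disorders are defined as "time to the first Read code or prescription indicating the outcomes by 14 years old". The section also accepts that recording quality affects validity, since musculoskeletal malformations are dropped "because they are not reliably recorded in GP records".

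The covariates in 4.3.3 begin with "maternal characteristics at baseline (i.e. age at child birth, problematic alcohol use, illicit drug use, recent tobacco use, and obesity" and continue with pregnancy and baby variables. None is a practice, region or area term. Section 4.4.1 builds the propensity score "conditional on the covariates described above, with the use of logistic-regression models", and on standard errors it says "To account for the clustering of siblings and multiple births within mother, robust standard errors will be estimated".

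Section 4.4.2 lists four sensitivity analyses: a pre-pregnancy negative control, a restriction to respiratory infections, stricter outcome definitions for cerebral palsy and malformations, and a live-birth-bias simulation. None stratifies on, matches on or clusters by practice.

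**The concern.** If practices that favour macrolides also code more completely, or serve populations at higher risk, a comparison pooled across practices attributes part of that difference to the drug. If they code less completely, the drug looks safer than it is. Balance checks on the listed covariates cannot show an imbalance in a factor that is not among them.

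At stake is an alternative explanation for a drug-safety result that no planned analysis isolates. Ten outcomes are tested without multiplicity adjustment, so a modest bias shared across outcomes could surface as a signal in the more precisely estimated ones.

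**Working it through.** **Inputs from the plan (4.5).** About 10,000 macrolide and 100,000 penicillin pregnancies; baseline risks of 0.002 (cerebral palsy and three malformation groups) to 0.02 (any major malformation) among included outcomes; target risk ratio 2, 80% power, 5% significance.

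**The plan's own figure.** The two-sided arcsine formula with 100,000 penicillin pregnancies gives a required macrolide group of 6,046 at risk 0.002, 558 at 0.02 and 12,892 at 0.001. Against the 10,000 cut-off this reproduces the inclusion decisions in Table 2. Practice plays no part in these figures.

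**Inputs that are assumptions.** The documents give none of the following:
- s_u, the between-practice SD of the log-odds of choosing a macrolide: 0.3 to 0.8
- s_v, the between-practice SD of the log recorded outcome rate: 0.2 to 0.4, with 0.6 as an extreme
- rho, their correlation: any sign
- number of practices: 200 to 700, as stated at each step

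**Step 1: bias in a crude risk ratio when the truth is 1.** The bias factor is approximately exp(rho × s_u × s_v).

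| s_u | s_v | rho | Apparent RR |
|---|---|---|---|
| any | any | 0 | 1.00 |
| 0.5 | 0.4 | 0.3 | exp(0.06) = 1.06 |
| 0.5 | 0.4 | 0.5 | exp(0.10) = 1.11 (simulated 1.10) |
| 0.5 | 0.4 | −0.3 | exp(−0.06) = 0.94 |
| 0.5 | 0.4 | −0.5 | exp(−0.10) = 0.90 (simulated 0.91) |
| 0.8 | 0.6 | 0.5 | exp(0.24) = 1.27 (simulated 1.25) |

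**Step 2: bias against precision.** SE of log RR = √[(1−p)/(10,000p) + (1−p)/(100,000p)], taking equal risk p in both groups.

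| Risk | SE of log RR | RR 1.06 to 1.10, in SEs |
|---|---|---|
| 0.002 | √(0.0499 + 0.0050) = 0.234 | 0.25 to 0.41 |
| 0.006 | √(0.0166 + 0.0017) = 0.135 | 0.43 to 0.71 |
| 0.02 | √(0.0049 + 0.0005) = 0.073 | 0.79 to 1.30 |

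**Step 3: effect on false positives.** This was simulated under a true null with 110,000 children in 500 assumed practices, without covariates or sibling clusters, at s_u 0.5, s_v 0.4 and rho 0.5.
- Risk 0.02: the crude RR is 1.10 and is declared significant in 31% of runs. Clustering the standard errors on practice leaves 29%. A practice-stratified Mantel-Haenszel RR gives 1.00 and 5.0%.
- Risk 0.002: the crude RR is 1.10, significant in about 8% of runs; stratified, 0.99 and about 5%.

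**Step 4: standard errors alone.** Variance inflation is 1 + (m − 1) × ICC of exposure × ICC of outcome, with m the mean practice size. For 200 to 700 practices and an exposure ICC of 0.01 to 0.06, the SE grows by under 1.5% at risk 0.002 and by 0.3% to 14% at risk 0.02.

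**Step 5: cost of comparing within practice.** Information kept = [mean p(1−p) within practice ÷ overall p(1−p)] × (1 − 1/m), where p is now the probability of a macrolide. With 675 assumed practices, m = 110,000/675 ≈ 163, and the odds of a macrolide are centred on 0.10. This gives 98.6%, 97.1% and 93.0% at s_u of 0.3, 0.5 and 0.8. The corresponding SE increases, 1/√(information kept), are 0.7%, 1.5% and 3.7%.

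**The case against.** The strongest reply is that no bias has been shown. No practice-level SD or correlation comes from the documents, and at zero correlation the bias vanishes. This stands in full: a reader might infer that the planned estimates are biased upward, and the documents support neither the bias nor its direction.

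Second, the 1.06 to 1.10 is for a crude ratio, whereas the plan reports propensity-weighted estimates. Birth year, smoking, alcohol, drug use, obesity, depression, anxiety and treated chronic conditions partly reflect the population a practice serves and, being recorded by the practice, some of its coding habits. This also stands; the figures illustrate scale and do not predict what the planned analysis would show.

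Third, the negative control makes the same drug contrast before pregnancy, and study mothers must be registered from at least 50 weeks before conception. Stable practice differences should appear there too. That is a real partial safeguard, although its stated target is maternal characteristics. It cannot separate practice from maternal confounding, and it does not remove either from the primary estimate.

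Fourth, outcome definitions blunt the coding argument. Minor anomalies after 2005 are excluded, ADHD needs at least two occurrences, and a sensitivity analysis requires repeated or mother-and-child malformation diagnoses. This helps, but the stricter definitions still depend on practice coding, and that sensitivity analysis leaves out epilepsy, ADHD and ASD.

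A reader might also infer that mother-level clustering is itself what lets practice differences pass as a drug effect. It is not: standard errors neither create nor remove bias, and Step 4 shows their effect is small for rare outcomes.

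**Conclusion.** The gap is real and cheap to close, but it is an improvement and not a proven fault. The documents establish that practices supply both exposure and outcome, that the identifier is held, and that no planned analysis compares children within practice. They do not establish how far practices differ, or whether preference and recording move together.

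If they do, at SDs of 0.5 and 0.4 and a correlation of 0.3 to 0.5 in either direction, a crude null ratio would move to about 1.06 to 1.10, or down to about 0.94 to 0.91, before any reduction by the covariates. That is far below the design ratio of 2. It is around one standard error for any major malformation and well under half of one at risk 0.002, so the practical exposure lies with the commoner outcomes. The main omission is the within-practice comparison; the clustering level is secondary.

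**What to change.** **In 4.4.2**, add a within-practice sensitivity analysis: the weighted Cox model stratified by practice ID for neurodevelopmental disorders, and a practice-stratified Mantel-Haenszel weighted risk ratio for malformations. Report it beside the primary estimate. Describe any shift as consistent with between-practice confounding, and name the alternatives: chance, changed stratum weights, and covariate imbalance within practice (the propensity weights are estimated without practice). A shift should not be labelled in advance as confounding. State also that the negative control will be read for practice-level as well as maternal confounding.

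**In 4.4.1**, as a secondary change, cluster the robust standard errors on practice, within which mothers are largely nested.

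**Cost.** SAP wording, two model options and a little extra analysis, using an identifier already held. The primary point estimate is unchanged. The stratified analysis gives up about 1 to 7% of the information under the Step 5 assumptions, and primary intervals may widen slightly from practice-level clustering.
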